8.1.3 Resistance Analyses

The following analyses will be performed for subjects in Arms 1 and 2A who do not achieve SVR₁₂ and who have post-baseline resistance data available: The HCV NS3 and NS5A amino acid sequences from the sample closest in time after virologic failure or treatment discontinuation with an HCV RNA level of ≥ 1000 IU/mL will be determined by population sequencing or NGS, and a listing by subject of all substitutions at GLE and PIB signature amino acid positions relative to the appropriate prototypic reference sequence of NS3 and NS5A will be provided.

8.1.4 Secondary Clinical Outcomes

Secondary clinical outcome analyses will be performed for subjects prior to kidney transplant in both Arms 1 and 2, and post kidney transplant for those who receive a kidney transplant in Arms 1 and 2. For details on safety reporting and periods of safety reporting see section 6.1.4.

The cumulative incidence function curves of time to kidney transplant will be created for each type of kidney transplant (Arms 1, 2A, 2B), and cumulative incidence and standard error (SE) will be calculated for each type of kidney transplant.

An exploratory analysis will create cumulative incidence function curves of time to kidney transplant for the subgroups of Arm 2B if sufficient subjects are enrolled in Arm 2B.

The number and percentage of subjects with clinical outcomes while on waitlist and after study consent (SAEs, delisting from waitlist, death) among subjects who receive an HCV RNA-positive kidney (Arm 1) and among those subjects who do not receive an HCV RNA-positive kidney (all Arm 2 subjects) overall and with breakdown by category of Arm 2 (2A, 2B, 2C). In addition, the total number of inpatient hospital days while on waitlist in those who did receive an HCV RNA-positive kidney (Arm 1) and total inpatient hospital days in those who did not (Arm 2) overall and with breakdown by category of Arm 2 will be summarized descriptively with mean, median, standard deviation (SD), minimum and maximum.

We will match MYTHIC trial participants 1:3 to comparators derived from the Organ Procurement and Transplantation Network database. Matching will be based on demographics and baseline characteristics known to influence waiting time, including waiting list priority, blood group, geographic region, and sensitization. A comparison of time to kidney transplantation between the kidney transplant candidates enrolled in the MYTHIC trial and OPTN comparators will be performed using a Cox proportional hazards model.

Clinical outcomes post-transplant will include death, graft failure, acute allograft rejection, delayed graft function, ALT elevation > 5 times the upper limit of normal, and SAEs. In addition, HCV-infection related events of fibrosing cholestatic hepatitis and extrahepatic manifestations of HCV infection collected for Arm 1 subjects and only for Arm 2A subjects who develop HCV viremia will also count as clinical outcomes. The number and percentage of subjects with each and any clinical outcomes will be summarized for those who receive an HCV RNA-positive kidney (Arm 1) versus Arm 2 subjects combined and broken down (2A and 2B) as applicable. The difference in the overall percentage of subjects with clinical outcomes post-transplant in Arm 1 vs Arm 2A + 2B will be assessed by logistic regression with Arm as a factor and including appropriate covariates to adjust for possible differences between Arms including waiting list priority, blood group,

geographic region and sensitization, as appropriate given sample size and other statistical considerations. In addition, to include any clinical outcomes due to being treated with G/P, another summary of clinical outcomes post-transplant will include any study drug (G/P) related severe treatment emergent adverse events for Arm 1 subjects, and another will include events of treatment emergent Grade ≥ 3 laboratory values and related severe treatment emergent adverse events as clinical outcomes for Arm 1 subjects.

Analyses of the eGFR outcome will be calculated eGFR using the 4-variable MDRD equation. Mean (SD) eGFR will be summarized at appropriate visits and compared between Arms. Specifically, mean eGFR at 24 weeks/6-months post-transplant and 1 year post transplant will be compared between Arm 1 transplant recipients and the combined group of Arm 2A and 2B transplant recipients (2B1-2B4). As a secondary approach, mean eGFR at 24 weeks/6-months post-transplant will be compared between Arm 1 recipients and Arm 2A and 2B kidney recipients limited to those 2A and 2B recipients who did not develop HCV infection.

We will also compare estimated proteinuria between Arms 1 and 2A, including a count of individuals with >1000 mg/day estimated proteinuria. Proteinuria will be estimated using spot protein:Cr ratio.

An exploratory analysis will summarize the number and percentage of subjects with clinical outcomes post kidney transplant for the subgroups of Arm 2B.

Exploratory analyses will also make comparisons between groups in which recipients of non study-eligible HCV RNA-positive and non study-eligible RNA-negative/HCV Ab-positive kidneys are censored at transplantation.

These clinical outcomes post-transplant will be further summarized by relatedness to study drug or HCV infection for Arm 1 subjects, and relatedness to transplant for each group Arm 1, Arm 2A, and Arm 2B subjects.

In addition, for subjects in study Arm 2 receiving HCV antibody-positive/ HCVRNA-negative kidneys, the rate and timing of HCV transmission will be summarized.

8.1.5 Safety Analyses for Arm 1

Adverse events will be coded using the Medical Dictionary for Regulatory Activities (MedDRA). Subjects reporting more than one adverse event for a given MedDRA preferred term will be counted only once for that term using the most severe grade for the severity grade table and the most related for the relationship to study drug table. Subjects reporting more than one type of event within a SOC will be counted only once for that SOC. An adverse event will be considered treatment-emergent if it begins or worsens in severity after initiation of study drug through 30 days post-study drug dosing. Related adverse events are those considered at least possibly related to study.

Laboratory data will be summarized from the first dose of G/P through 2 days post dosing. Laboratory values will be rated according to the National Cancer Institute Common Terminology Criteria for Adverse Events (NCI CTCAE Version 4) which is available on the Cancer Therapy Evaluation Program (CTEP) website at:
http://evs.nci.nih.gov/ftp1/CTCAE/CTCAE_4.03_2010-06-14_QuickReference_8.5x11.pdf
Grade 3+ laboratory values are those that are Grade 3 or 4.

8.1.6 Additional Adverse Event Analyses for Arm 1

For subjects treated with G/P, the number and percentage of subjects with treatment-emergent adverse events (i.e., any event that begins or worsens in severity after initiation of study drug through 30 days post-study drug dosing) will be tabulated by primary MedDRA System Organ Class (SOC) and preferred term (PT) for each treatment arm. The tabulation of the number of subjects with treatment-emergent adverse events by severity grade and relationship to study drug, kidney transplantation, or HCV infection also will be provided.

8.1.7 Additional Clinical Laboratory Data for Arm 1

Clinical laboratory tests will be summarized by transplant phase (e.g., awaiting a transplant, after receipt of a transplant) and treatment arm. Additional evaluations will be performed for subjects who received study drug as part of the protocol (Arm 1). The baseline value will be the last non-missing measurement prior to the initial dose of study drug. Mean changes from baseline to each post-baseline visit, including the Final Treatment Visit, will be summarized descriptively for Arm 1 as feasible.

In addition, the number and percentage of subjects with post-baseline laboratory values of interest equal or greater than Grade 3 of the CTCAE scale will be summarized overall and by Arm.

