A “standard of care” transplant will be defined as any of the following kidney transplants: a deceased donor HCV RNA-positive kidney transplant that did not meet donor criteria for Arm 1 or HCV RNA-positive kidney transplant that place after last transplant allowed for Arm 1 but met criteria for Arm 1 inclusion (2B1); a deceased donor HCV RNA-negative/HCV Ab-positive kidney transplant that either did not meet donor criteria or took place > 6 months after the last Arm 1 transplant (2B2); a deceased donor HCV RNA-negative/HCV Ab-negative transplant at a MYTHIC clinical site (2B3); any living donor kidney transplant at a MYTHIC clinical site (2B4); or any kidney transplant at a different center than the 7 clinical sites (2B5).

In addition, to compare the total number of inpatient hospital days while on the waitlist and after study consent in those who did receive a study-eligible HCV RNA-positive kidney (Arm 1) vs total inpatient hospital days in those who did not (Arm 2) overall and with breakdown by the 3 categories of Arm 2 (2A, 2B and 2C).

- 3) To describe clinical outcomes and data post-transplant (death, graft failure, acute allograft rejection, delayed graft function, estimated glomerular filtration rate [eGFR], proteinuria, ALT elevation > 5 times the upper limit of normal (ULN), SAEs) between those who receive an HCV RNA-positive kidney (Arm1) and in subjects who receive an HCV RNA-negative/HCV Ab-positive kidney allograft (Arm 2A) or a standard of care kidney transplant (from Arm 2B1 – 2B4) combined and separately. For subjects of Arm 1 and Arm 2A who become HCV infected, we will collect additional clinical outcomes of sclerosing cholestatic hepatitis and extrahepatic manifestations of HCV. In addition, the clinical

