The primary efficacy endpoint is sustained virologic response 12 weeks post dosing (SVR₁₂), defined as HCV RNA < LLOQ 12 weeks after the last actual dose of G/P. The SVR₁₂ rate will be determined from all enrolled subjects who received an HCV RNA-positive kidney in Arm 1 and received at least one dose of G/P study drug along with a two-sided 95% confidence interval. The confidence interval for the SVR₁₂ rate will be calculated using Wilson's score method.

The secondary efficacy endpoints for recipients of kidney transplants from HCV RNA-positive donors in Arm 1 are:

1. The percentage of subjects with on-treatment virologic failure;
2. The percentage of subjects with post-treatment virologic relapse.

Additional efficacy analyses will be performed.

Clinical endpoints:

Secondary endpoints for the secondary objectives are:

1. Among all subjects enrolled in the study who receive a kidney transplant, the time to kidney transplant and cumulative incidence of each type of transplant will be determined for: study-eligible HCV RNA-positive kidneys (Arm 1), study-eligible HCV RNA-negative/HCV Ab-positive kidneys (Arm 2A), and standard of care kidney transplants (Arm 2B).
2. The number and percentage of subjects with clinical outcomes while on the

waitlist (SAEs, delisting from waitlist, death) among subjects who receive an HCV RNA-positive kidney in Arm 1 and among those subjects who do not receive a study eligible HCV RNA-positive kidney (all Arm 2 subjects) overall and with breakdown by the category in Arm 2 (2A, 2B and 2C). In addition, the total number of inpatient hospital days while on waitlist in those who did receive a study eligible HCV RNA-positive kidney (Arm 1) and total inpatient hospital days in those who did not (Arm 2) overall and with breakdown by categories of Arm 2 will be summarized descriptively.

3. The number and percentage of subjects with the following clinical outcomes and data post-transplant as applicable: death, graft failure, acute allograft rejection, delayed graft function, ALT elevations > 5x ULN, and SAEs. The difference in the overall percentage of subjects with clinical outcomes and data post-transplant between Arm 1 and Arms (2A + 2B1 – 2B4) will be assessed by logistic regression with Arm as a factor and appropriate covariates to adjust for possible differences between Arms including waiting list priority, blood group, geographic region and sensitization as appropriate.

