4.2 Secondary Objectives

The secondary objectives are:

- 1) Among all subjects enrolled in the study, to describe time to kidney transplant and cumulative incidence of each type of transplant: a study-eligible HCV RNA-positive kidney (Arm 1), a study-eligible HCV RNA-negative/HCV antibody-positive kidney (Arm 2A), or a kidney transplant performed as part of standard of care treatment (Arm 2B).

2) To describe clinical outcomes while on the waitlist after consent (Serious Adverse events [SAEs], delisting from waitlist, death) between those who receive a study-eligible HCV RNA-positive kidney (Arm 1) and in subjects consented for this study who do not receive a study-eligible kidney transplant from an HCV RNA-positive donor (all Arm 2 subjects) overall and with breakdown by the 3 categories of Arm 2 as below:

A: subjects who receive a kidney from a study-eligible HCV RNA-negative/HCV Ab-positive donor

B: subjects who receive a standard of care kidney transplant

C: subjects who were not transplanted within 1 year of consent

Hereafter, these categories will be referred to as Arms 2A, 2B and 2C.

A “standard of care” transplant will be defined as any of the following kidney transplants: a deceased donor HCV RNA-positive kidney transplant that did not meet donor criteria for Arm 1 or HCV RNA-positive kidney transplant that place after last transplant allowed for Arm 1 but met criteria for Arm 1 inclusion (2B1); a deceased donor HCV RNA-negative/HCV Ab-positive kidney transplant that either did not meet donor criteria or took place > 6 months after the last Arm 1 transplant (2B2); a deceased donor HCV RNA-negative/HCV Ab-negative transplant at a MYTHIC clinical site (2B3); any living donor kidney transplant at a MYTHIC clinical site (2B4); or any kidney transplant at a different center than the 7 clinical sites (2B5).

In addition, to compare the total number of inpatient hospital days while on the waitlist and after study consent in those who did receive a study eligible HCV RNA-positive kidney (Arm 1) vs total inpatient hospital days in those who did not (Arm 2) overall and with breakdown by the 3 categories of Arm 2 (2A, 2B and 2C).

3) To describe clinical outcomes and data post-transplant (death, graft failure, acute allograft rejection, delayed graft function, estimated glomerular filtration rate [eGFR], proteinuria, ALT elevation > 5 times the upper limit of normal (ULN), SAEs)

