8.3 Assignment of Participants to Study Arms: Methods

This is a two-arm study. All eligible subjects who entered the study will be observed. Observed subjects who accept a study-eligible HCV RNA-positive kidney allograft offer will be assigned to the G/P treatment Arm 1 and followed in that Arm up until 1 year post-transplant. All other enrolled study subjects will remain in Arm 2 of the study (see Figure 1A).

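### Waitlist deaths, delisting and hospital days are tabulated by an arm that is fixed only at transplant, so Arm 1 waitlist deaths are zero by definition and hospital-day totals follow waiting time

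*Protocol*

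**What the plan says.** Protocol 8.1.4 reports "The number and percentage of subjects with clinical outcomes while on waitlist and after study consent (SAEs, delisting from waitlist, death) among subjects" in Arm 1 and in Arm 2, with Arm 2 split into 2A, 2B and 2C. The same section summarizes hospital use by arm, giving the mean, median, SD, minimum and maximum. The Arm 2 quantity is worded as "total inpatient hospital days in those who did not (Arm 2) overall and with breakdown by category of Arm 2"; its Arm 1 counterpart, unlike it, is limited to time on the list: "the total number of inpatient hospital days while on waitlist in those who did receive an HCV RNA-positive kidney (Arm 1"). Clinical endpoint 2 in the Synopsis has the same layout: "waitlist (SAEs, delisting from waitlist, death) among subjects who receive an HCV RNA-positive kidney in Arm 1" against all Arm 2 subjects.

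Objective 2 (Synopsis and section 4.2) uses two verbs. For SAEs, delisting and death the aim is to describe. For hospital days it is "to compare the total number of inpatient hospital days while on the waitlist and after study consent" between arms.

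On arm membership, section 8.3 states: "Observed subjects who accept a study-eligible HCV RNA-positive kidney allograft offer will be assigned to the G/P treatment Arm 1". All other enrolled subjects stay in Arm 2. Section 4.2 defines the third Arm 2 category as "C: subjects who were not transplanted within 1 year of consent".

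The draft summary SAP treats Arm as time-dependent for hospital admissions (Parts 6 and 7, with a rate per 100 patient-years in Part 6) and for SAEs (Part 15). Its death row (Part 10) covers Arm 1 only. Waitlist death on its own, delisting and hospital days have no row.

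**The concern.** The outcomes occur before transplant, but the grouping is decided by the transplant. Subjects are sorted by whether they lived and stayed listed long enough to receive a particular kidney, and their waitlist survival is then tabulated by that sorting. This is immortal-time bias in its plainest form.

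Hospital days have a related fault. Arm 1 waitlist time stops at transplant, whereas an untransplanted Arm 2 subject keeps accumulating it for at least a year. A total per subject therefore mixes the rate of hospital use with the length of the wait, which is already the subject of objective 1.

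The rationale for the trial is that HCV-infected kidneys shorten the wait. A table with no Arm 1 waitlist deaths and fewer Arm 1 hospital days could be read as a benefit of accepting such kidneys even if there were none.

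**Working it through.** The plan gives no expected count, rate or power for these outcomes, so there is no figure of its own to reproduce.

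**Step 1: death.** Arm 1, 2A and 2B each require a transplant, and a recipient was alive at the end of the wait. Waitlist deaths in these groups are 0 by definition; all fall in the not-transplanted group. No assumption is needed.

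**Step 2: delisting.** A permanently delisted subject is not transplanted from the list, so the same logic applies. Someone delisted, relisted and then transplanted can appear in Arm 1, so this zero is not exact.

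**Step 3: hospital days when there is no arm effect.**

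Inputs from the documents: 90 enrolled and about 40 transplanted in an estimated 6 months (8.2); 30 Arm 1 transplants as the target (Synopsis); Arm 2 followed for at least 1 year (5.1).

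Assumptions, not in the documents: constant hazards identical for everyone; 3 of every 4 transplants in Arm 1; a combined death and permanent-delisting hazard m of 0.04 to 0.20 per year; waitlist observation cut at 1 year; one common hospital-day rate, which cancels from the ratio.

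The total transplant hazard is H = −ln(1 − 40/90)/T: 1.176 per year for T = 0.5, and 0.588 for T = 1 as a slower variant. With Λ = H + m and q = exp(−Λ), and ignoring the limit of 30:

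- mean Arm 1 wait: w1 = 1/Λ − q/(1 − q)
- share in Arm 1: p1 = (0.75H/Λ)(1 − q)
- mean wait, everyone: w = (1 − q)/Λ
- mean Arm 2 wait: w2 = (w − p1·w1)/(1 − p1)

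For T = 1, m = 0.04: Λ = 0.628, q = 0.534, w1 = 0.448, p1 = 0.327, w = 0.743, w2 = 0.886 years; w2/w1 = 1.98.

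For T = 0.5, m = 0.20: Λ = 1.376, q = 0.253, w1 = 0.389, p1 = 0.479, w = 0.543, w2 = 0.685 years; w2/w1 = 1.76.

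The second case implies 0.479 × 90 ≈ 43 Arm 1 subjects, more than the planned 30. Simulation of 90 subjects with Arm 1 closed after the 30th transplant, m from 0.05 to 0.20 and an assumed 10 hospital days per patient-year gives:

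| Setting (3:1 split) | Arm 1 days | Arm 2 days | Ratio |
|---|---|---|---|
| 40 of 90 by 6 months, all enter together | 2.4 | 7.5–8.2 | 3.1–3.5 |
| Same, entry spread over 12–18 months | 2.9–3.2 | 7.4–8.1 | 2.3–2.8 |
| 40 of 90 by 12 months, all enter together | 4.2 | 8.1–8.8 | 1.9–2.1 |
| No limit of 30 (formula above) | – | – | 1.8–2.0 |

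Other splits widen this. From 50:50 to 90:10 with simultaneous entry, the ratio runs 1.7–4.8 in the 6-month setting and 1.75–2.5 in the 12-month setting.

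**Step 4: does a denominator repair it?** For hospital days, yes in this model: days divided by waitlist patient-years give 10.0 in both arms. For death it does not, because the Arm 1 numerator stays at 0. Death and delisting need the whole cohort from consent.

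**The case against.** The strongest reply is that these are descriptive tables. Objective 2 says describe for death and delisting; 8.1.4 and Synopsis endpoint 2 say the hospital days are summarized descriptively; no test, interval or model is attached. The 2A/2B/2C breakdown would also make the artefact visible to a careful reader. This stands and limits the severity. It does not remove the point, because objective 2 does compare hospital-day totals, and describing an outcome in a group where it cannot occur tells the reader nothing.

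A second reply is that section 8.1 leaves details to the SAP, and Parts 6 and 7 may be its version of the hospital-use objective. That is possible, since the SAP is a draft summary. But those Parts count admissions, not days; Part 15 includes deaths only pooled with other SAEs; and delisting appears nowhere. Either the 8.1.4 tables stand, or part of a stated secondary objective has no analysis.

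A reader might also infer that Arm 2 totals include post-transplant days, since the Arm 2 clause, "vs total inpatient hospital days in those who did not (Arm 2) overall and with breakdown by the 3 categories of Arm 2", does not repeat the waitlist restriction. The documents do not support this. The Safety part of the Synopsis lists hospital days among outcomes collected on the waiting list, and sections 5.1.10, 5.3.4 and 6.1.4 place non-SAE hospitalizations in that phase. The omission needs only a clarification.

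**Conclusion.** Wrong as written, for three secondary outcomes. The zero for waitlist deaths in Arm 1, 2A and 2B is exact and rests on the arm definitions alone. For delisting it holds only when delisting is permanent.

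The hospital-day distortion is certain in direction when hazards are equal, but its size is illustrative: roughly 2 to 3 times more days per subject in Arm 2, about 1.8 to 3.5 across the settings at a 3:1 split. A reader might take the 3.1–3.5 result as the effect to expect. It assumes all 90 subjects enter together, whereas section 5.1.5 ends enrollment only after the 30th Arm 1 transplant, which fits staggered entry and a smaller ratio.

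These are expectations. At an assumed event hazard of 0.03 per year, 13–18% of single trials of 90 would show no waitlist events in Arm 2 either. The primary SVR12 analysis is unaffected.

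**What to change.** 1. Add a SAP row reporting waitlist death and delisting for all enrolled subjects from consent, as cumulative incidence with transplant as a competing event. Parts 4 and 5 already use this method for transplant.
2. Add a SAP row reporting hospital days per patient-year on the waitlist for the whole cohort. If a by-arm display is kept, give days per waitlist patient-year by eventual arm, marked as descriptive. Time-dependent Arm, as in Parts 6 and 7, will not serve here: a subject enters Arm 1 at transplant, so Arm 1 would have no waitlist time.
3. In objective 2, replace the comparison of totals with this rate. Repeat the waitlist restriction for Arm 2 in the Synopsis, 4.2 and 8.1.4.
4. If the by-arm table stays, state beside it that waitlist deaths in Arm 1, 2A and 2B are zero by definition and that it supports no Arm 1 versus Arm 2 comparison.

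The cost is wording and two or three summary rows, using data the Synopsis already says are collected from all subjects on the waiting list. The downside is that the by-arm waitlist contrast is given up or caveated. Conduct, sample size and the primary endpoint do not change.
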